1. PURPOSE OF THE STUDY

a. Brief Summary

The overarching goal of this research program is to elucidate causal and directional neural network-level abnormalities in depression, and how they are modulated by an individually-tailored, circuit-directed intervention.

b. Objectives

To examine the impact of antidepressant rTMS on causal network abnormalities in depression, and the relationship between baseline networks deficits and clinical outcome.

c. Rationale for Research in Humans

This is a study of Major Depressive Disorder in humans.

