2. STUDY PROCEDURES

a. Procedures

All eligible subjects will undergo structured diagnostic interviews, including a MDD-specific assessment at Stanford shortly after recruitment. Subjects will then have a pre-treatment baseline MRI session (structural, resting), a concurrent fMRI/TMS scan session and a concurrent EEG/TMS session within two weeks at one of the Stanford scan sites. Preparation for physiological measurements will take 30-40 minutes including calibration time. These initial assessments provide a baseline for comparing pre- to post-treatment brain changes in patients. In the case of the baseline assessments, TMS is a probe for testing brain circuitry and as such, actual TMS must be used. All participants, whether randomized to active or sham, complete the TMS baseline assessments in order to provide baseline brain activation profiles.

After determining study eligibility, participants will wear an EEG cap which is like a swimming cap with Ag/AgCl electrodes which will be filled with gels through syringe. The Ag/AgCl electrodes for EOG.

Subjects will then be randomized to receive 4 weeks daily rTMS vs. sham (placebo) treatment sessions (total 20). For participants who receive sham (placebo) treatment for the first 4 weeks, they are offered 4 weeks of open-label active treatment. For participants who receive active

treatment during the first 4 weeks of treatment, they are not offered another 4 weeks of treatment.

Finally, another fMRI/TMS scan and EEG/TMS session will be scheduled within one week post rTMS treatment. Depression and anxiety will be evaluated using MDD and anxiety specific assessment pre and post- rTMS/sham treatment and after the 10th and 20th (and 30th and 40th for open-label patients) treatment session during rTMS/sham.

Patients who drop out of treatment will be encouraged to return for clinical and imaging assessments. Participants who continue onto the open-label treatment will also come in for another fMRI/TMS scan and EEG/TMS session within 1 week after their second 4 weeks of treatment.

b. Procedure Risks

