In summary, TMS (single-pulse TMS and rTMS) are generally safe and well-tolerated, however, seizures remain a rare but significant adverse event. In our study, all stimulation parameters are determined to comply with the safety guidelines for TMS (Wasserman, 1998; Rossi et al., 2009). In the event of adverse effects related to MRI/fMRI scanning and TMS, safety coordinators and medical staff at the Lucas Center and CNI will be on-site for consultation and assistance. The Stanford University Hospital Emergency Room is less than a 5-minute walk from the Lucas Center or 10 minutes from CNI. Finally, [name], the PI of this study, is a licensed physician and will oversee all research clinicians and monitor any adverse situations that might arise during the course of 20-40 sessions of rTMS at the psychiatry outpatient clinic, as well as the MRI/fMRI scans.

c. Use of Deception in the Study

Not applicable

d. Use of Audio and Video Recordings

Not applicable

e. Alternative Procedures or Courses of Treatment

The alternative to participation is not participation.

f. Will it be possible to continue the more (most) appropriate therapy for the participant(s) after the conclusion of the study?

This will not be possible. Daily rTMS treatment for MDD is intended to be a brief course of intervention. We do offer open-label rTMS to patients in sham group.

g. Study Endpoint(s)

The endpoint of the study is fMRI/TMS scans post rTMS treatment. Although this study involves rTMS and sham treatment, our goal is to explore the brain circuit involved in clinical improvement in response to focal, non-invasive brain stimulation with rTMS, not the efficacy of rTMS vs sham. In addition, we do offer open-label rTMS to the sham group.

Primary Outcome Measure:

Clinician administered HAM-D

The Hamilton Depression Rating Scale (HAM-D) is a 24-item clinician-administered assessment utilized as a way of determining a patient's level of depression before, during, and after treatment. It takes approximately 15-20 minutes to complete the interview and score the results.

Exploratory Outcome Measures:

fMRI/TMS assessed neural network connectivity [Time Frame: Up to 3 months.] From pre- to post-treatment, improvement will be based on enhanced functional connectivity.

Implicit emotion regulation [Time Frame: Up to 3 months]

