10. STATISTICAL ANALYSIS PLAN

For the depression group, t-tests and ANOVAs will be performed to examine the effect of rTMS treatment, compared to sham, on network activity by comparing the follow-up TMS/fMRI scan to the initial scan between those two groups (N=20/group) – doing so will determine the network changes associated with real rTMS, since we have a convincing sham control arm. Additionally, we will use multiple regressions to examine the relationship between network-level activity change and clinical response to rTMS treatment in the real treatment group. Baseline TMS/fMRI moderators of treatment response will be examined using multiple regressions in the real treatment group.

Power calculation: Not Applicable.

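### Baseline moderators are to be tested in the active arm alone, which can show prediction under rTMS but not moderation of the rTMS effect

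*Combined protocol and SAP*

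**What the plan says.** Section 10 contains three analyses. The first compares network change between rTMS and sham and justifies attributing that change to real rTMS by the control: "since we have a convincing sham control arm". The second relates network change to clinical response within the active arm. The third is the one at issue: "Baseline TMS/fMRI moderators of treatment response will be examined using multiple regressions in the real treatment group". No interaction term or sham-arm regression appears there or elsewhere in the document.

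The related objective in Section 1b is worded more modestly, as "the relationship between baseline networks deficits and clinical outcome". Section 2g disclaims a test of efficacy against sham and says "our goal is to explore the brain circuit involved in clinical improvement in response to focal, non-invasive brain stimulation with rTMS".

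The data for a two-arm analysis are already planned. Section 2a says: "All participants, whether randomized to active or sham, complete the TMS baseline assessments in order to provide baseline brain activation profiles". It also schedules depression ratings before and after treatment in both arms, and "after the 10th and 20th (and 30th and 40th for open-label patients) treatment session during rTMS/sham". Sham patients may then cross over: "For participants who receive sham (placebo) treatment for the first 4 weeks, they are offered 4 weeks of open-label active treatment".

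**The concern.** The analysis named and the analysis specified are different things. Moderation concerns how the treatment effect varies with a baseline marker, and that effect is a contrast between arms. With one arm there is no contrast. A patient whose baseline network profile goes with a good outcome under rTMS might have done equally well on sham through natural course, regression to the mean or placebo response.

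The harm is one of interpretation. Section 2g lists the network measures as exploratory (although it also calls the post-treatment fMRI/TMS scans the study endpoint), and no decision rule depends on this regression. But the stated goal is the circuit involved in improvement in response to rTMS, and a purely prognostic marker reported as a moderator would mislead on exactly that point. The error can also run the other way: a marker related to outcome only under sham is a true moderator that the planned analysis cannot see.

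**Working it through.** **Inputs from the documents.** 20 per group (Section 10), 40 in total (Section 5a); 2 × 20 = 40 agrees. There is no power figure to reproduce: "Power calculation: Not Applicable".

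**Assumptions (not in the documents).** One standardised marker M; outcome Y is HAM-D at the end of the randomised phase; r is the marginal correlation of M with Y; M is unrelated to baseline HAM-D (B); pre-post HAM-D correlation 0.4 unless varied; two-sided 5% level; no dropout.

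**1. What each analysis estimates.** Let the mean of Y be α₁ + β₁M under active and α₀ + β₀M under sham.

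- Treatment effect at marker value M: (α₁ − α₀) + (β₁ − β₀)M.
- Moderation means β₁ − β₀ ≠ 0.
- The planned regression tests β₁ = 0. If β₁ = β₀ ≠ 0 there is no moderation, yet the test tends to reject. If β₁ = 0 and β₀ ≠ 0 there is moderation, yet it rejects only at the 5% level.

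**2. How often a marker with no moderation is significant.** In each arm, Y = rM + 0.4B + √(1 − r² − 0.16)·e. With n = 20 the critical correlation is 2.101/√(18 + 2.101²) = 0.444. Simulated rejection rates with equal slopes in both arms:

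| r in both arms | Active only, unadjusted | Active only, adjusted for baseline HAM-D | Arm × marker, both arms |
|---|---|---|---|
| 0.1 | 7% | 7% | 5% |
| 0.2 | 13–14% | 14% | 5% |
| 0.3 | 25% | 28% | 5% |
| 0.4 | 43% | 48% | 5% |
| 0.5 | 64% | 71% | 5% |
| 0.6 | 84% | 90% | 5% |

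**3. The reverse case.** With r = 0 under active and 0.5 under sham, the active-only test rejects in 5% of trials and the adjusted interaction test in 40%.

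**4. What the two-arm model can detect at 20 per arm.** Model: Y on arm, B, M and arm × M (35 residual degrees of freedom).

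| Active r vs sham r | Power, pre-post r 0.4 | Power, pre-post r 0.2 to 0.6 | n per arm for about 80% (pre-post r 0.4) |
|---|---|---|---|
| 0.3 vs 0 | 16% | – | – |
| 0.5 vs 0.2 | 18% | – | – |
| 0.5 vs 0 | 40% | 35–51% | 50 |
| 0.6 vs 0 | 56% | 49–71% | 33 |
| 0.7 vs 0 | 73% | 65–87% | 24 |

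Without baseline HAM-D in the model, the last three powers are 35%, 49% and 64%. With 16 per arm after dropout, the 40% falls to about 31%.

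**5. Precision.** For 0.5 vs 0, the residual variance averages (0.59 + 0.84)/2 = 0.715. The standard error of the slope difference is about √(0.715 × 2/17) = 0.29, so the 95% half-width is about 2.03 × 0.29 = 0.59. The simulated median is 0.58. Across the cases of 0.5 to 0.7 vs 0, the half-width is 0.53 to 0.58 standardised units.

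**The case against.** The best reply is that this is a matter of wording. The Section 1b objective asks only for an association between baseline deficits and outcome, Section 2g disclaims efficacy against sham, and Section 10 openly names the active arm as the population. Read as prediction among treated patients, the planned regression answers the objective, and changing one word would cure the defect. The two-arm model, by contrast, has little power: about 16% for 0.3 vs 0, and lower still with dropout or several markers. The rates in the first table rest on assumed correlations, are small when the prognostic correlation is 0.1 or 0.2, and measure no error unless a hit is called moderation.

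Much of this stands. The objective can be met by prediction, renaming is a sufficient minimum, and the rates illustrate a point of logic. It does not rescue the text as written, because Section 10 promises moderators and specifies an analysis that cannot identify them. Disclaiming an efficacy test does not turn a one-arm slope into effect modification. Low power is a reason to report the interaction as an estimate with its interval; it gives no licence to draw the claim from a test that does not address it.

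**Conclusion.** The concern holds. Followed as written, the plan would report a one-arm association as moderation. That conclusion follows from the definition and needs no numerical assumption. The size of the risk does: it runs from about 7% at a prognostic correlation of 0.1 to about 84% at 0.6 in the unadjusted test, for one marker with 20 per arm and no dropout. The consequence is a possible misreading of an exploratory result, with no effect on safety or on any decision rule. It should be fixed, and fixing it is cheap.

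**What to change.** In Section 10, replace the active-only moderator regression with a model in both randomised arms: HAM-D after session 20 on arm, baseline HAM-D, baseline network marker and arm × marker. Section 10 does not define clinical response; HAM-D is proposed because Section 2g names it as the primary outcome, and session 20 because it closes the randomised phase. Report each arm's slope and their difference with 95% confidence intervals, labelled exploratory. Keep the term moderator for the interaction and predictor for the active-arm slope. State that ratings after sessions 30 and 40 are not used for the sham slope, since by then those patients are in the open-label active phase.

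If the two-arm model is not adopted, change moderators to predictors of outcome under active rTMS.

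The cost is SAP wording and one extra model per marker, with no new data. The drawback is the low interaction power shown above: a null interaction at 20 per arm would be uninformative, and the SAP should say so.
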